### **3.3.4 Potential Limitations of Simulated Interventional Study**

Given that the intervention in this study is simulated, there is no risk of harm to patients through incorrect testing decisions. However, the lack of intervention means that the impact on the eventual prescription cannot be assessed, because prescriber behaviour is not incorporated. Future randomised interventional studies will therefore need to be performed to assess impact before the approach could be deployed in the clinical setting. Another potential limitation is missing data, either from patients who have been transferred from outside of the region, or who have passed through areas without electronic prescribing data (e.g., Accident and Emergency, Intensive Care). Although this will be a small proportion of the antibiotics prescribed and administered, the potential impact of this will need to be considered when the model is explained. An ability to distinguish between transfer from out of area (for example, a high AMR setting) and patients presenting to healthcare for the first time may also affect the predictive value of an apparent lack of healthcare exposure for a lower AMR probability by diluting its effect. Some antimicrobial susceptibility data will also be missing due to agents not having been tested; the impact of this will need to be weighted within the process of algorithm development.

## **3.4 Economic evaluation of ADAPT-AST**

## ADAPT-AST Protocol

A decision model will be developed to estimate the cost and health outcomes associated with using ADAPT-AST to inform clinical decisions about the treatment of UTI in hospitals, compared to standard care (as observed within the Liverpool data). The introduction of ADAPT-AST is intended to allow patients to receive earlier access to appropriate therapy by better targeting the use of antibiotic susceptibility tests. This has the potential to identify early a larger set of antibiotics to which an individual is susceptible. This avoids the cost and health impacts of delayed appropriate therapy, and by expanding the choice of therapies allows clinical teams to prioritise between these therapies based on other important factors: namely toxicity profile; mode of administration; risk of AMR; and anticipated differences in efficacy.

The economic evaluation will compare the AST Decision Making Algorithms evaluated within the simulated interventional trial to standard care. A conceptual model will be developed in consultation with relevant stakeholders (e.g. clinicians who treat UTIs, microbiologists) to identify how the AST information available under different AST Decision Making Algorithms (and under standard care) is likely to influence antibiotic prescription, and how this is likely to modify costs and outcomes amongst patients treated for UTIs in UK secondary care. The conceptual model will also identify which health and cost effects of introducing ADAPT-AST should be prioritised for modelling based on their likely importance for patient health and costs. This conceptual model will then form the basis for a more detailed model protocol documenting the model structure and data sources for the quantitative model.

The susceptibility information expected to be available to inform clinical decision making under ADAPT-AST and standard care will be obtained from the clinical prediction model and simulated interventional study. An important consideration for the economic evaluation will be how this information influences clinical decision making. This will be informed by data from the Liverpool area dataset where feasible, supplemented by the literature and clinical opinion where necessary. The decision model will reflect the short-term costs of introducing ADAPT-AST in terms of clinical time, infrastructure and microbiology tests. The long-term cost implications of using ADAPT-AST to guide clinical decision making will be reflected accounting for impacts on length of stay and intensity of care within hospitals (e.g. requirement for IV antibiotics, significant treatments for antibiotic-related toxicity, use of ICU/HDU). The short- and long-term implications of using ADAPT-AST for patient health will be quantified as quality-adjusted life years (QALYs) which account for both morbidity and mortality effects, and can reflect both efficacy and toxicity effects of antibiotics. We will separately quantify the expected impact of using ADAPT-AST and standard care on the proportion of patients receiving treatment with an antibiotic falling under the WHO Access, Watch and Reserve categories.

Categorisation of patients receiving multiple agents will be established in discussion with experts. Cost, quality of life and mortality parameters will be obtained from a combination of the Liverpool area dataset, the literature and expert opinion where necessary.

Model results will be summarised as incremental cost-effectiveness ratios (ICERs) and net health effects and an assessment of whether ADAPT-AST represents a cost-effective use of NHS resources will be provided, appropriately accounting for health opportunity costs. The sensitivity of the model results to important data inputs and assumptions will be tested using deterministic sensitivity analysis and probabilistic sensitivity analysis.

## 4 ETHICAL AND REGULATORY CONSIDERATIONS

### 4.1 Assessment and management of risk

There is no interventional component to the study; there is therefore no risk of direct harm to individuals. The risks to consider at study outset are breaches in Information Governance, Data Protection and Data Security. The processes for obtaining appropriate regulatory approval and ensuring that such breaches do not occur are detailed in sections 4.2.1 and 4.6 of this protocol. Six-monthly central monitoring milestones of risk will be put in place at which point the risk assessment will be updated. Risk assessments will also be updated if a protocol deviation occurs. If data quality or quantity is insufficient at the first annual milestone, a substantial amendment will be submitted to amend the route of data access.

### 4.2 Regulatory Review and Amendments

#### 4.2.1 Ethical and Regulatory Review, Compliance and Reports

The study will be conducted in accordance with the principles of Good Clinical Practice (GCP). Before the start of the study, LUHFT Sponsorship, Cheshire and Merseyside ICB/CIPHA data asset and access group (DAAG – see Section and research ethics committee (REC) approval will be secured by the CI.

#### 4.2.2 Amendments

A study management group (SMG) will be convened and chaired by the CI with representation from across the study team and a public lay representative to provide ongoing management and oversight, support amendments and deal with reporting, data issues and protocol deviations. It is the sponsor's responsibility to decide whether an amendment is substantial or non-substantial. If a substantial amendment to the protocol is required, the chief investigator (CI) or delegate will submit a valid notice of amendment to the sponsor for consideration via the appropriate route. Amendment history will be tracked by keeping all protocol versions in a secure password-protected folder in the LUHFT computer system. Substantial amendments will not be implemented until all necessary regulatory approvals have been formally approved.

#### **4.4 Patient & Public Involvement**

In 2022, an AMR Citizens' Jury was commissioned by the University of Liverpool to explore public and patient perspectives on collaborative monitoring of AMR data for applications of this kind in the Liverpool area(36). Jurors were recruited by advertisement and selected to provide a representative cohort of the Liverpool city area. They were provided with subject matter background on AMR, data protection and information governance by domain experts over several days. They were then asked to discuss and provide their assessment of the acceptability, design, management, undertaking, research, analysis and dissemination of the results of integrated data systems used to facilitate clinical care, drug development and research. The jury was broadly supportive of the use of integrated regional pseudonymised data for this process and raised important points about the legal, security and quality frameworks that will be required to underpin healthcare data projects of this kind.

#### **4.5 Protocol compliance**

All Protocol deviations will be recorded and reviewed as part of regular SMG meetings and reported to Sponsor where deemed appropriate.

#### **4.6 Consent, data protection and patient confidentiality**

Pre-existing Population Health DPIAs have been signed by data controllers for healthcare data to be transferred to the ICB/CIPHA secure data environment (SDE) within Cheshire and Merseyside ICB firewalls, to perform routine data linkage and pseudonymisation. Only pseudonymised, non-identifiable data will be accessed by researchers with approval from ICB/CIPHA DAAG. Patients who opted out of

data sharing for purposes other than direct care (Type 1 objections) are excluded from the flow of data into the ICB/CIPHA SDE. The study will adhere to LUHFT and CIPHA governance structures for data protection and patient confidentiality to ensure compliance to legal standards. As study sponsor, Liverpool University Hospitals NHS Foundation Trust is the overriding governance structure.

#### **4.6.1 Data Access via CIPHA**

The data access and cleaning processes are detailed in Section 3.1. Core project datasets will be curated and maintained from the integrated healthcare records detailed in section 3.1.2, where available. An application for access to the data within CIPHA will be made through the CIPHA Data Asset and Access Group (DAAG). CIPHA are an NHS Population Health platform established during the COVID-19 pandemic which will provide the software, tools, compute, and governance for project access. Approval will be obtained from DAAG for CIPHA to permit access of the ADAPT-AST team to pseudonymised data (pseudonymised by NHS Data Services for Commission Regional Offices [DSCRO] according to standard policies) in the CIPHA secure data environment. This environment is administered by CIPHA. CIPHA meets requirements of GDPR, The Data Protection Act 2018 and the NHS Data Security and Protection Toolkit, and is certified to ISO27001, ISO9001 and Cyber Essentials standards.

The legal basis for the study under General Data Protection Regulation (GDPR) is Article 9(2)(j), in that data processing and access is necessary for the purpose of scientific or statistical purposes in accordance with Article 89(1). Data controllers, the third party (NHS Cheshire and Merseyside ICB/CIPHA) and investigators must comply with the requirements of the Data Protection Act 1998 with regards to the collection, storage, processing, and disclosure of personal information and will uphold the Act's core principles. Only the minimum amount of data pertaining to the minimum number of individuals required to facilitate the study methodology will be used. Pseudonymisation keys are kept secure within an encrypted, password protected ICB/CIPHA data warehouse and only accessible by an ICB/CIPHA engineer assigned to data linkage and pseudonymisation (not accessible by the research team). The details of the pseudonymisation process are listed in Section 3.1.4. The data flow diagram for ADAPT-AST is displayed in Figure 6.

## ADAPT-AST Protocol

[figure not shown]

Figure 6: ADAPT-AST data flow diagram. DAAG and LUHFT approvals will facilitate portal access to pseudonymised LUHFT and GP data within the NHS CIPHA SDE.

Access to the pseudonymised datasets will be limited to members and collaborators of the study group. Access will be password protected by NHS or UoL IT security. The pseudonymised data will be stored for 10 years after publication, in accordance with the UK Research and Innovation (UKRI) best practice recommendations (UK Research and Innovation, 2018). A data catalogue will be maintained. The data custodian will be the CI, and will be responsible for the safe custody, transport and storage of any aggregate data resulting from this project.

#### **4.6.2 Confidentiality**

The Chief Investigator will preserve the confidentiality of participants taking part in the study and will abide by the Data Protection Act 2018 and the UK GDPR as amended from time to time and any successor legislation in the UK and any other directly applicable regulation relating to data protection and privacy.

#### **4.6.3 Audits**

The study may be subject to inspection and audit by LUHFT under their remit as sponsor and other regulatory bodies to ensure adherence to GCP and the UK Policy Framework for Health and Social Care Research (v3.2 10th October 2017).

### **4.7 Indemnity**

LUHFT holds Indemnity and insurance cover which will apply to this study.

### **4.8 Access to the final study dataset**

The final study dataset will be accessible to the CI and the data scientists performing the data analysis, and the CIPHA engineer(s) facilitating access to the pseudonymised data.

## **5 END OF STUDY**

The end of study will be when analysis of the simulated interventional study data on the final ADAPT-AST algorithm version is complete, at which point an End of Study Declaration will be completed and submitted to the Sponsor. After the end of study is declared no study activity, other than final analysis of the data (following 'lock' of the study database) and report writing, will be undertaken.

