Study Title	Adaptive Prediction of Antimicrobial Susceptibility and its Implementation to Improve the Management of Urinary Tract Infection
Internal ref. no. (or short title)	ADAPT-AST (Adaptive Antimicrobial Susceptibility Testing)

Study Design	Retrospective observational study
Study Participants	Demographic, antimicrobial prescribing and microbiology specimen data from patients >18 years in the catchment area served by Liverpool University Hospitals NHS Foundation Trust and Liverpool Community Health
Planned Size of Sample (if applicable)	> 250,000 specimens estimated (the number of patients will be fewer because some patients will have had more than one specimen sent)
Outcomes	
Primary outcome:
 
The number of antimicrobial susceptibility results that 'should' spur action by a clinician on the day that actual first-line AST results were reported (in green on Figure 5).
 
Secondary outcomes:
 
 
1. The number of days until a result that 'should' spur action by a clinician (in green on Figure 5).
 
2. The number of antimicrobial susceptibility results that 'could' spur action by a clinician on the day that actual first-line AST results were reported (in yellow on Figure 5).
 
3. The number of days until a result that 'could' spur action by a clinician (in yellow on Figure 5).
 
4. The projected health economic cost per specimen, including laboratory (e.g., consumable cost) and patient (e.g., drug toxicity, clinical failure) measures guided by the above criteria.
 

Follow up duration (if applicable)	Not applicable
Planned Study Period	3 years
Project Question/Aim(s)	
 
1. Can causal, explainable Bayesian causal inference (BCI) approaches be used to develop/(re)validate (train/test) clinical prediction models for prediction of urine organism antimicrobial susceptibility using NHS care data?
 

	2. Can the resulting ADAPT-AST adaptive, informatics-based (data-driven and system-wide) approach target AST for UTI better than existing approaches can, thereby improving timeliness of clinical decision making and saving resources through efficiency?
--	---

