### **3.1.5 Data Cleaning**

Once researchers have been given access to the data, cleaning of the dataset will be required because:

- Intrinsic resistance patterns will be populated in the dataset according to European Committee on Antimicrobial Susceptibility Testing (EUCAST) rules to enable proper interpretation (for

instance, amoxicillin will not be tested on most *Klebsiella* species because of intrinsic resistance, but this will be a blank in the starting dataset, which will need to be filled in with an 'R')(50)

- Organisms susceptible at increased antimicrobial exposure 'I' can be interpreted as susceptible in the context of urinary tract infection according to EUCAST rules(51). They will therefore be reclassified as 'S' to facilitate the use of binary LR (see below).
- Resistance data from multiple organisms grown in the same specimen will be inputted in the same way as for individual growth, but organisms will remain linked by pseudonymised specimen number to facilitate trial of composite 'functional' resistance of multiple organism growth as an input (i.e., if either organism in the specimen is resistant report the specimen as 'R', if both are susceptible report as 'S').
- Some data elements (for instance specimen site) will have been recorded manually and there may therefore be typographical errors that require correction to make them statistically processable.
- Assessment of data completeness will be required and strategies for managing missing data developed.
- Other data transformations may need to occur to facilitate processability or economise on computing power, e.g., feature scaling or dimensionality reduction(52).

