## **3.3 Development and Clinical Evaluation of ADAPT-AST in a simulated clinical setting**

### **3.3.1 AST Decision Making Algorithm Development**

The final stage of the project will be evaluating the potential clinical and resource impact of the testing framework on the same 20% of samples used in the testing dataset above. To do this, a clinically suitable AST decision making model first will need to be developed. Comparison of a range of algorithmic approaches is likely to be required, but the aim of the first decision model trialled will be to select 7 antimicrobials for testing (the number in the standard first-line panel currently tested under existing LCL SOPs). The antimicrobials that will be initially eligible for AST selection are those for which probability calculations will be outputted, listed above in Table 2.

The first prioritisation approach trialled will be to rank antimicrobial choices in descending order of susceptibility uncertainty except for cefpodoxime and cefoxitin, then to apply an algorithm in Figure 4 to ensure that a mixture of oral and intravenous agents is tested.

[figure not shown]

Figure 4: Algorithm used to select 7 antimicrobials from the sorted shortlist.

\*Amoxicillin, Amoxicillin-Clavulanate, Aztreonam, Cefalexin, Ceftazidime, Phenoxycephalothin, Piperacillin-tazobactam.

Cefpodoxime or cefoxitin are not used as treatments in the local area, but resistance to either antimicrobial indicates a high probability of resistance mechanisms which preclude use of some beta lactams (BL) and beta-lactam-beta-lactamase-inhibitor combinations (BL-BLIC)(57,58). Therefore, the algorithm will also be designed for cefpodoxime and cefoxitin to only be tested when their susceptibility is sufficiently uncertain (a defined classification threshold will be calculated for this) and there is a chance of the affected BLs / BL-BLICs, cefpodoxime and cefoxitin all being tested as part of the panel of 7.

No additional weighting, ranking or exclusion criteria will initially be applied, but depending on evaluation based on a priori microbiology / clinical / health economic knowledge, measures may need to be taken to further steward the AST choices. These may include exclusion of certain antimicrobial choices which are less practically useful for UTI but for which resistance uncertainty may be high (e.g., teicoplanin) or algorithmic prioritisation/exclusion/weighting measures for factors such as WHO

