### Primary outcome:

The number of antimicrobial susceptibility results that 'should' spur action by a clinician on the day that actual first-line AST results were reported (in green on Figure 5).

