## **6 DISSEMINATION POLICY**

### **6.1 Dissemination policy**

The data arising from the study will be owned by the study authors. On completion of the study, the data will be analysed and tabulated, and a Final Study Report prepared, which will be accessible on the Centres for Antimicrobial Optimisation Network (CAMO-NET) website. Participating investigators

can publish any of the study data with permission of the CI. Public participants of the Liverpool AMR Citizens' Jury will be informed of the outcome of the study by provision of the publication. All statistical and BCI code used to generate the results will be made available open source, shared via a GitHub public repository following journal publication.

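### Section 5 is circular on analysis, database lock and end of study, and does not require a lock before the primary ADAPT-AST versus SOP comparison is known

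*Protocol*

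**What the plan says.** Protocol section 5 defines the end point of the study: "The end of study will be when analysis of the simulated interventional study data on the final ADAPT-AST algorithm version is complete". An End of Study Declaration is then submitted to the sponsor. After it, no activity is allowed "other than final analysis of the data (following 'lock' of the study database) and report writing". The protocol mentions a database lock nowhere else.

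Section 6.1 gives a second account: "On completion of the study, the data will be analysed and tabulated, and a Final Study Report prepared".

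The simulated study produces the primary outcome, defined in section 3.3.2 as "The number of antimicrobial susceptibility results that 'should' spur action by a clinician on the day that actual first-line AST results were reported". Section 3.3.1 says that the evaluation is made "on the same 20% of samples used in the testing dataset above".

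Section 3.1.5 places cleaning at the time when researchers gain access to the data. It fixes two recoding rules: intrinsic resistance is filled in as R, and I is reclassified as S. Other matters are left for later: "Assessment of data completeness will be required and strategies for managing missing data developed". Manual entries may be corrected, and further transformations may be applied.

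**The concern.** A lock protects a result only if it comes before anyone has seen that result. The data here are retrospective, both panels are run by computer on the same specimens, and the team's own code classifies each result as should, could or cannot be actioned. No masking of the analysts is described. In that setting, freezing the data, code and algorithm before scoring is one of the main safeguards against choices made with the answer in view.

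The protocol calls for a lock but attaches it to an undefined *final analysis* that follows the completed primary comparison. A later reader could not show from the protocol that the cleaning rules and the algorithm version were settled before the ADAPT-AST versus SOP result was known. The end-of-study definition also fails in its own terms, because a further analysis of the data remains to be done once it is met.

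**Working it through.** No arithmetic applies, and the protocol gives no figure to reproduce. The check sets the statements side by side and asks which orders of events they allow.

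Call the four events:
- **A**: simulated-study analysis on the final algorithm complete (section 5)
- **E**: end of study (section 5)
- **L**: database lock (section 5)
- **F**: final analysis (section 5)

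**Step 1. What section 5 orders.** A triggers E. F is listed among what may happen after E, so A → E → F. L comes before F. Nothing states the order of L and A.

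**Step 2. Which sequences remain.**
1. A → E → L → F. The primary comparison is known before the lock.
2. L → A → E → F. The lock comes first and protects the comparison.

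The first is the natural reading. The lock appears only in a parenthesis qualifying F, in the sentence about what happens after the declaration. The second is possible, but nothing in the document requires it.

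**Step 3. What section 6.1 adds.** It puts analysis after completion of the study. If that analysis is A, section 6.1 says E → A while section 5 says A → E, which is a contradiction. If it is F, the two sections agree, but F is then the analysis feeding the Final Study Report and A is a completed earlier look at the same outcome. The protocol does not say which is meant.

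**Step 4. What is still adjustable when A is run.**
- Section 3.1.5: the missing-data strategy is still to be developed, corrections and transformations are open-ended, and a composite resistance coding for specimens with several organisms is to be tried. No freeze point is given.
- Section 3.3.1: several decision algorithms are expected to be compared. Exclusions, weightings and prioritisation may be added in the light of evaluation.
- Section 3.2.2: the 20% set is also used to assess and refine the prediction models.
- Section 3.3.4: how untested susceptibilities are handled is left to algorithm development.
- The extent of the dataset is described in two ways: five years from 17 May 2017 (section 3.1.3), and from 17 May 2017 to the present (section 3.2.1).

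**Step 5. Scale of the set concerned.** With the planned minimum of 250,000 specimens, the hold-out is 0.20 × 250,000 = 50,000 and the training set 0.80 × 250,000 = 200,000. This bears on the fix: the training set is large enough to hold an internal tuning split.

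**The case against.** *The text does not place the lock after the primary analysis.* Correct. A reader might infer that section 5 fixes that order, but it says only that the lock precedes the final analysis. The supportable statement is that no lock is required before the primary comparison.

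*Cleaning does not stay open after the result is known.* A reader might infer that it does. The document does not say so. Cleaning is planned at data access, ahead of training and simulation, and section 5 itself bars activity other than final analysis and report writing after the declaration. What stands is narrower: no point is given, before the comparison is run, at which the missing-data rules, corrections and selection rules become fixed.

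*The final analysis may be something else.* The economic evaluation in section 3.4 takes inputs from the simulated study and could be what is meant. That is possible, since the term is undefined. It does not remove the circularity or supply a lock before the primary comparison.

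*Lock procedure belongs in the SAP.* Much of the detail does, and its absence alone would not be a finding. But the end-of-study trigger and its relation to lock and analysis are fixed in the protocol, where they conflict.

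*The effect on the result could be calculated.* A reader might reason that, with so many specimens, recoding a very small share of results could decide significance. The documents do not support a figure. They give no standard deviation for the between-panel difference, and section 3.3.3 plans an exact Poisson test where its distributional check allows, not a paired comparison of these counts. Because both algorithms run on every specimen, recoding a result present in both panels would largely cancel.

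**Conclusion.** The concern holds in a limited form. Sections 5 and 6.1 are circular: completed analysis ends the study, yet analysis follows the end of the study. The only lock belongs to that later analysis. The protocol therefore does not secure a lock before the primary comparison is known, and its natural reading puts the lock afterwards, while cleaning, missing-data and selection rules carry no freeze point.

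This is a weakness in safeguards, of moderate weight and worth correcting before analysis starts. It is not evidence that the result will be biased, and no size of bias can be derived. The conclusion rests on the wording of sections 5, 6.1, 3.1.5 and 3.3.1 and on no numerical assumption. It would fall away if a governing document already required the lock before the hold-out comparison, though sections 5 and 6.1 would still need reconciling.

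**What to change.** Rewrite section 5 in this order:
1. Compare and tune algorithms within the 80% training data, for example by cross-validation or an internal split.
2. Lock and time-stamp the cleaned dataset (including its date range and missing-data rules), the list of hold-out specimens, the should/could classification code and the final algorithm version.
3. Only then score the final ADAPT-AST versus SOP comparison on the 20% hold-out.
4. Declare end of study once the section 3.3.3 and 3.4 analyses are complete, leaving only report writing.
5. Document any later unlock with its reason, and report the pre-unlock result beside the new one.

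Align section 6.1 so that completion follows analysis, and adjust sections 3.2.2 and 3.3.1 so that refinement is not done on the hold-out.

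The cost is a short amendment and a frozen copy in the secure data environment. No new data are needed. There are two real downsides. Genuine errors found after lock need a documented unlock. Tuning must also move off the hold-out, which changes the workflow in sections 3.2.2 and 3.3.1 and leaves somewhat less of the training data for model fitting if an internal split is used.
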